7.3 Visit Time Windows

Table 7.3.1 presents the visit window assigned for scheduled efficacy and safety assessments scheduled for every 12 weeks and the corresponding range of treatment days (window) during which an actual visit may occur.

Period	Visit	Scheduled Visit Day	Window			
First 48-Week Treatment Period	Baseline	Day 1	$Days \le 1$			
	Week 12	Day 85	Days [2, 127]			
	Week 24	Day 169	Days [128, 211]			
	Week 36	Day 253	Days [212, 295]			
	Week 48	Day 337	For subjects entered into continuation period Days [296, start of continuation period-1] For subjects did not enter into continuation period Days \geq 296			
Treatment Weeks 50-240	Week 60	Day 421	Days [start of continuation period, 463]			
	Every 12 Weeks	Day 84x ^a +421	[380+84x,463+84x]			
	Week 144	Day 1009	$Days \ge 968$			

Table 7.3.1:Visit Time Windows

a x=1,2...6

Termination visit for subjects who didn't complete the study, and unscheduled visits will be mapped to the closest post baseline scheduled visits if the scheduled visits are missing. If there are more than one unscheduled/end of study visits mapped to the same window, the one closer to the target day will be used. If more than one visit has the equal distance to the target day then the later one will be used, if more than one visits on the same day, use the time or the sequence number to select the later record. For listings and shift tables, all data points will be included.

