- w. The MPS HAQ or HAQ/CHAQ should be performed for *UX003 treatment-naïve subjects and subjects enrolling from the MPS 7 Phase 3 Ultragenyx sponsored study UX003-CL301*. The MPS HAQ will be administered to all age groups. The CHAQ should be performed for pediatric subjects only (<14 years old). The HAQ should be performed for subjects ≥14 years old. Subjects will consistently complete the same questionnaire (HAQ or CHAQ) administered at baseline for the duration of the study regardless of whether their age changes from 13 to 14 during the study. The age-appropriate version of the PedsQL multidimensional fatigue module will be administered throughout the study. *For subjects enrolling from previous clinical trial with UX003*, these subject-reported outcome measures will only be administered if they were previously performed in their primary (or feeder) study.
- x. As part of the subject/parent/caregiver clinical global impression assessment, subjects/parents/caregivers will be asked to provide narratives of how treatment has impacted the subject's ability to complete activities of daily living.
- y. Liver and spleen size will be assessed qualitatively by physical examination.
- z. The termination visit should be completed by all subjects who do not complete the Week 144 end of study visit. The termination visit should be completed within 30 days of the last dose of study drug. Efficacy assessments performed within 30 days will not be repeated at the termination visit. AEs ongoing at 30 days following the last dose of study drug should have a comment in the source document by the Investigator that the event has recovered, recovered with sequelae, or stabilized. If the termination visit occurs after Week 48, blood for serum biomarkers of inflammation will not be collected and BOT-2 assessments will not be conducted.

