The therapeutic ERT doses in prior successful programs for other MPS disorders (0.58, 0.5 and 1 mg/kg weekly for MPS 1, 2, 4A, and 6, respectively) were based on comparable doses that exhibited efficacy in their respective animal models. PK data in MPS 1, MPS 2, MPS 4A, and MPS 6 subjects demonstrate that doses of 0.2 to 2 mg/kg are adequate to achieve enzyme concentrations of ~10-27 nM in the circulation. These enzyme levels are approximately 10- to 30-fold the uptake constants (1-2.7 nM) for the mannose 6 phosphate receptor and are believed to saturate delivery of enzyme to the tissues (Kakkis et al. 1994), (Kakkis et al. 1996a), (Kakkis et al. 2001), (Dvorak-Ewell et al. 2010). Similar uptake constants (1.2-2.6 nM) were obtained in studies with human MPS 7 fibroblast cells in vitro (Ultragenyx data). Studies with rhGUS in MPS 7 mice at doses of 4 mg/kg show that serum GUS concentrations of >10-fold the uptake constant were readily achieved and demonstrated that enzyme was delivered to a variety of important tissues, implying that the efficacious dose should be within this range (Grubb et al. 2008).

A higher dose is needed to provide the same rhGUS molar concentration as other MPS enzymes, since rhGUS enzyme has two active sites per tetramer and the molecular weight (332 kDa tetramer) is approximately 4-fold higher compared to the other MPS enzymes. The equivalent number of moles of enzyme active sites would require about two

times the efficacious dose for other MPS enzymes on a mass or milligram basis. Therefore, approximately 1-4 mg/kg UX003 is estimated to achieve the same molar concentration of active enzyme.

The QOW dosing regimen is supported by the long in vitro half-life and increased stability of rhGUS compared with other MPS enzymes. Data from the earliest MPS ERT studies showed that when human enzymes for MPS 1 or 2 were applied to deficient human fibroblasts, the half-life of the enzyme in the lysosome was on the order of 2-5 days (Kakkis et al. 1994), (Elaprase 2006) leading to weekly dosing frequency as the optimal choice. For rhGUS, this experiment showed a half-life of about 40 days, which is a substantial increase over MPS 1 or MPS 2 enzymes, which are dosed weekly. The rhGUS enzyme is also a more stable enzyme than the other MPS enzymes at neutral pH, as it might be exposed to the circulation before uptake by lysosomes. Both the increased half-life and stability of rhGUS indicate QOW dosing should be adequate in humans.

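### SAP Table 7.3.1 divides Week 48 from Week 60 at the start of a continuation period that CL202 does not have, so termination and unscheduled values near those visits can be placed in two ways

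*SAP*

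**What the plan says.** Table 7.3.1 in SAP 7.3 gives numeric windows for every 12-weekly visit except at one boundary. The Week 48 row (target Day 337) has two rules. One is "For subjects entered into continuation period Days [296, start of continuation period-1". The other begins "For subjects did not enter into continuation period Days" and runs from Day 296 with no upper limit. The Week 60 row (target Day 421) is "Days [start of continuation period, 463". Weeks 72 to 132 follow the formula "380+84x,463+84x" with x from 1 to 6, and Week 144 starts at Day 968. The second block of the table is labelled "Treatment Weeks 50-240".

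Three other rules bear on how a value gets its visit:

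- SAP 7.2 analyses scheduled visits by visit number.
- SAP 7.3, below the table, states "Termination visit for subjects who didn't complete the study, and unscheduled visits will be mapped to the closest post baseline scheduled visits", on condition that the scheduled visit is missing. SAP 7.1 says the mapping is based on target days.
- Footnote z of Protocol Table 2.1 states "The termination visit should be completed within 30 days of the last dose of study drug". It also says that efficacy assessments done within 30 days are not repeated at that visit.

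**The concern.** Neither document defines a continuation period for CL202. Protocol 7.1 and SAP 3.2 describe a single course of up to 144 weeks. Both schedules of events divide it only into the first 48 weeks and Weeks 50 to 144. A programmer therefore has no date for the Week 48/60 boundary and must choose a reading. The readings differ from one another, and most differ from the closest-visit rule in the same section.

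At stake is the placement of termination and unscheduled values collected between the Week 48 and Week 60 targets. uGAG and physical examination are the relevant assessments, because both are 12-weekly. For uGAG the choice also affects the model: SAP 8.7 fits a generalized estimating equation (GEE) to percent change with visit as a factor, so the rule can determine whether a value contributes and at which visit.

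**Working it through.** **Inputs.** Target days and window limits come from SAP Table 7.3.1, the mapping rules from SAP 7.1 to 7.3, and the termination and no-repeat rules from Protocol Table 2.1, footnote z. The start of the continuation period is not given. I assume Day 338 (the day after the Week 48 target) or Day 351 (Week 50: 7 × 50 + 1).

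**Reproducing the table.** Target day = 7 × week + 1, which gives 85, 169, 253, 337, 421 and so on to 1009. All 12 targets match. Each limit is the midpoint of adjacent targets, with the midpoint day in the earlier window:

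- Weeks 12/24: (85 + 169)/2 = 127; table 127/128.
- Weeks 36/48: (253 + 337)/2 = 295; table 295/296.
- Weeks 60/72: (421 + 505)/2 = 463; table 463/464.
- Weeks 132/144: (925 + 1009)/2 = 967; table 967/968.

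All 10 numeric limits reproduce. The eleventh is Weeks 48/60: (337 + 421)/2 = 379, so the limit should be 379/380. The table's own formula at x = 0 gives the same answer: [380 + 0, 463 + 0] = [380, 463], around target 421.

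**Table against closest target day**

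| Reading of the boundary | Week 48 window | Week 60 window | Days where the table differs from the closest visit |
|---|---|---|---|
| Start Day 338 | 296–337 (42 days) | 338–463 (126 days) | 338–378 (41 days) |
| Start Day 351 | 296–350 (55 days) | 351–463 (113 days) | 351–378 (28 days) |
| Start Day 380 | 296–379 (84 days) | 380–463 (84 days) | none |
| No subject enters the period | 296 onward | overlapped | 380–1009 (630 days) |

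Weeks 24, 36 and 72 to 132 all have 84-day windows. For each assumed start day there is no disagreement from Day 464 onward. In the last row, the open Week 48 window overlaps all eight later visits.

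**Effect on one uGAG value.** Suppose Week 48 is done on Day 337 and termination is on Day 370.

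1. Days since the last uGAG: 370 − 337 = 33. This exceeds 30, so the no-repeat rule does not apply and a sample is due.
2. Distances to targets: 370 − 337 = 33 to Week 48, and 421 − 370 = 51 to Week 60.
3. By the text, the closest visit is Week 48. It is not missing, so the value is not mapped.
4. By the table with a start of Day 338 or 351, Day 370 lies in the Week 60 window. Week 60 is missing, so the value enters the GEE model as Week 60.

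**How often this can arise for uGAG.** With Week 48 on target, the no-repeat rule covers termination up to Day 337 + 30 = 367, so the disputed days are 368–378, which is 11 days. If the Week 48 sample was missed, the whole 28- or 41-day band is in dispute. A Day 365 sample, for instance, is 28 days from Week 48 and 56 from Week 60; the text gives Week 48 and the table gives Week 60.

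**The case against.** The strongest reply is that the rules that do the work never use the continuation period. Scheduled visits keep their visit number, and termination and unscheduled values go to the closest target day only when the scheduled visit is missing. On that view the table is redundant at this boundary and the matter is one of wording. The reply adds that the natural reading treats the second block as simply following the first 48 weeks, and that listings and shift tables keep all data points.

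Much of this stands, and it limits the reach of the point. It does not remove the conflict. SAP 7.3 resolves competing records among those mapped to the same window, so the windows are operative. The table is introduced as assigning windows to scheduled assessments, while the visit-number sentence sits under a heading on missing dates. Even the natural reading, with the second block starting at Week 50, conflicts with the closest-visit rule on 28 days. Two competent programmers could produce different Week 60 summaries from the same data.

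A reader might also infer that termination samples taken off drug dilute the uGAG result and should be excluded, say beyond 14 + 3 = 17 days after the last infusion. The documents do not support this:

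- Footnote c of Protocol Table 2.1 allows ±7 days at major visits. A compliant scheduled sample can be 14 + 7 = 21 days after the last dose, or 24 if the preceding infusion was 3 days early.
- Protocol 7.4.3 says "For rhGUS, this experiment showed a half-life of about 40 days". If that held in vivo, enzyme at 30 days would be 2^(−16/40) = 76% of its 14-day level. This is in vitro enzyme, not uGAG, and shows no dilution of the endpoint.
- Removing the last values of subjects who discontinue, in a study of about 20, could itself cause selective missingness.

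**Conclusion.** The point holds at one boundary. The Week 48/60 limit cannot be programmed as written, and on a start of Day 338 or Day 351 it contradicts the SAP's closest-visit rule on 41 or 28 days. Both start days are assumptions. The documents do not show how many subjects would have a termination or unscheduled value in that band, so the number affected is unknown.

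Two wider inferences should be resisted. First, a reader might conclude that values throughout Weeks 60 to 144 go to the wrong visit. That needs the literal reading in which no subject enters the period, which would leave the table's later rows without purpose; on the other readings the Week 72 to 144 windows are numeric and sound. Second, a reader might conclude that an early stop by the sponsor would put the last uGAG, antibody and safety values of the whole cohort at risk. Only subjects whose termination visit falls in the disputed band would be affected. The table covers 12-weekly assessments, and neither laboratory tests (Weeks 48, 96 and 144) nor antibodies (every 24 weeks) are due at Week 60.

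The consequence is therefore small, but the conflict is real and the correction is unambiguous.

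**What to change.** In SAP Table 7.3.1:

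- Set Week 48 to Days [296, 379] and Week 60 to Days [380, 463] for all subjects.
- Delete the split between subjects who did and did not enter a continuation period.
- Change the block label from Weeks 50-240 to Weeks 50-144.

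The table and the closest-visit rule then agree on every day, with the midpoint day kept in the earlier window as elsewhere in the table.

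At most, also list days since last dose for termination uGAG values that are mapped to a visit, and keep those values in the analysis.

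The cost is a few words in the SAP and, if the listing is added, one derived variable. No data collection changes. SAP version 1.0 covers the protocol only through Amendment 1, and the protocol is now at Amendment 3, so the edits can go into the same update.

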7.4 Software

SAS[®] software version 9.4 or higher will be used to perform most or all statistical analyses.

8 STATISTICAL METHODS OF ANALYSIS

8.1 General Principles

All analysis will be performed based on full analysis set, and summaries will be presented overall and for naïve, IST and rollover subjects separately. The statistical analyses will be reported using summary tables, figures, and data listings. Statistical tests will be 2-sided at the alpha =0.05 significance level. All p-values will be presented as nominal p-values. Continuous variables will be summarized with means, standard deviations, medians, minimums, and maximums. Categorical variables will be summarized by counts and by percentages of subjects in corresponding categories. All raw data obtained from the CRFs as well as any derived data will be included in data listings.

8.2 Subject Disposition

The subjects in the full analysis set will be summarized. The reasons for study discontinuation will be summarized.

8.3 Demographics and Other Baseline Characteristics

For rollover subjects, demographic parameters (e.g., age, sex, race and ethnicity) and other baseline characteristics (i.e., initial diagnosis, height and weight) measured at baseline of the feeder study will be used. For naïve subjects or IST subjects, demographic and other baseline characteristics measured at the baseline of this study will be used.

8.4 Medical History

Medical and MPS treatment history will be summarized. Medical and MPS treatment history for rollover subjects are recorded in the feeder study.

8.5 Prior and Concomitant Medications

The latest World Health Organization Drug (WHODRUG) dictionary will be used to classify prior and concomitant medications.

For rollover subjects, prior medication will be defined as any medication taken before the first dose in the feeder study. For naïve and IST subjects, prior medication will be defined as any medication taken prior to the first dose of the investigational product in this study.

Concomitant medication is defined as any medication taken during the study between the day of the first dose of the investigational product and the day of the last dose of the investigational product in this study.

The number and proportion of subjects receiving each reported prior and concomitant medication will be summarized by Anatomical Therapeutic Chemical (ATC) code and preferred term. Multiple uses by a subject of the same drug will be counted only once in the summary tables.

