#### 7.5.2.9 Concomitant Medications

Concomitant medications will be reviewed and recorded in the subject's CRF at each study visit, beginning at the Baseline visit.

For subjects enrolling from an Ultragenyx-sponsored clinical trial, medications (investigational, prescription, over-the-counter, and herbal) and nutritional supplements reported as ongoing at primary study's End of Treatment visit and any new medications taken prior to Baseline will be reviewed and recorded at Baseline visit. Any enrolling subject who had an early termination in the primary study will have their baseline concomitant medications collected in the same manner as a subject who is treatment naïve or enrolling from a non-Ultragenyx sponsored study (see following paragraph).

For subjects who are treatment naïve or who are enrolling from a non-Ultragenyx sponsored clinical trial, medications (investigational, prescription, over-the-counter, and herbal) and nutritional supplements taken during the 30 days prior to Baseline will be reviewed and recorded.

At each subsequent visit, change in medications since the previous visit will be recorded. A discussion of prior and concomitant medications is provided in Section 7.4.4.

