5.8 Duration of exposure to UX003

Duration of exposure to UX003 in days in this is defined as: last date of UX003 infusion – first date of UX003 infusion in this study + 14 days.

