An AE (classified by preferred term) will be considered a treatment emergent adverse event (TEAE) if it occurred on or after the first dose in this study, and was not present prior to the first dose in this study, or it was present at the first dose in this study but increased in severity during the study.

Subject incidence of TEAEs will be tabulated by SOC and preferred term. Serious adverse events (SAEs), treatment-related TEAEs and treatment-related SAEs will also be summarized.

Detailed listings for all AEs, SAEs, treatment related TEAEs, treatment related SAEs, AEs leading to the discontinuation, and death will also be generated. The severity will be based on Common Terminology Criteria for Adverse Events (CTCAE). If an AE cannot be graded based on CTCAE, the investigator will assign a severity based on 1 = mild, 2 = moderate, 3 = severe, 4 = life threatening, and 5 = Death related to AE.

Patterns of Infusion Associated Reactions (IARs) will be specifically evaluated throughout the study. IARs will be characterized into 4 distinct types based on timing of onset relative to the infusion and specific clinical manifestations: anaphylactoid, anaphylaxis, urticarial (with or without angioedema), and immune complex. Safety reporting of individual AEs will be recorded in parallel. Detailed listings of IARs will be provided.

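### SAP 8.5 closes concomitant medication on the day of the last infusion, so a drug new to the subject and first taken after that day is in no summary table, although the event it treats can count as a TEAE

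*SAP*

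**What the plan says.** SAP 8.5 recognises two classes of medication. Concomitant medication is "any medication taken during the study between the day of the first dose of the investigational product and the day of the last dose" in this study. For treatment-naïve and IST subjects, "prior medication will be defined as any medication taken prior to the first dose of the investigational product in this study"; for rollover subjects the cut-off is the first dose in the feeder study. The summary rule covers these two classes only: each "reported prior and concomitant medication will be summarized by Anatomical Therapeutic Chemical (ATC) code and preferred term", and repeated use of one drug by one subject counts once. No post-treatment class is described in SAP 8.5 or 8.8.

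Other windows in the same plan run later. SAP 8.8.1 treats an event as treatment-emergent "if it occurred on or after the first dose in this study, and was not present prior to the first dose in this study", or if it was present then and later worsened in severity; no end date is given. SAP 5.8 computes exposure as the last infusion date minus the "first date of UX003 infusion in this study + 14 days". SAP 7.2 caps imputed stop dates, for adverse events and medications alike, at study completion or discontinuation rather than at the last dose.

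Protocol 7.5.2.10 collects adverse events until 30 days after the last dose. Protocol 7.5.2.9 has medications recorded at every visit: "At each subsequent visit, change in medications since the previous visit will be recorded". Table 2.1 marks them at the Termination Visit, which under its footnote z is for subjects who do not complete Week 144 and should take place within 30 days of the last dose.

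**The concern.** Long-term safety is the primary objective, and protocol 7.5.2 and 7.6.6 name concomitant medications among the safety measures to be evaluated and summarised. The adverse event table and the medication table are normally read together: one shows what happened, the other what was needed to treat it. Under the SAP they stop at different points. An event with onset a few days after the final infusion can enter the TEAE table, while a drug started for it enters neither medication summary, even though the site recorded it at the Termination Visit. The subjects who have such a visit are those who leave before Week 144, so the omission falls mainly on early leavers, whose post-infusion treatment a safety reader would want to see.

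**Working it through.** The plan gives no figure for this gap, so there is none to reproduce. The check is a rule test followed by a day count.

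**Inputs.** Day 1 is the first infusion in this study. An infusion at Week w falls on day L = 1 + 7w. The medication window is Day 1 to Day L inclusive (SAP 8.5). The TEAE window starts on Day 1 (SAP 8.8.1) and has no stated end; its practical end is the collection limit, Day L + 30 (protocol 7.5.2.10).

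**Rule test, last infusion at Week 24 (L = 169).**

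- Drug first taken on Day 169: concomitant, tabulated.
- Drug taken on Days 50–60 and again on Day 175: tabulated once because of the earlier use; the later use changes nothing.
- Drug first taken on Day 170 or later: not before the first dose, so not prior; after the last-dose day, so not concomitant. It is in no summary table.
- New event with onset on Day 174: after the first dose and within 30 days of the last, so collected and treatment-emergent under SAP 8.8.1.

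**Day count.** The tail is (L + 30) − L = 30 days for every subject. As a share of the TEAE window it is 30 / (L + 30):

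| Last infusion | L | L + 30 | Share outside medication window |
|---|---|---|---|
| Week 0 (one infusion) | 1 | 31 | 96.8% |
| Week 2 (two infusions) | 15 | 45 | 66.7% |
| Week 12 | 85 | 115 | 26.1% |
| Week 24 | 169 | 199 | 15.1% |
| Week 48 | 337 | 367 | 8.2% |
| Week 142 | 995 | 1025 | 2.9% |
| Week 144 | 1009 | 1039 | 2.9% |

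**What is actually recorded in the tail.** Medications are recorded at visits. A subject who leaves early has the Termination Visit, at most 30 days after the last dose and possibly sooner. A completer dosed at Week 144 has no later scheduled visit, so little or nothing is recorded to be dropped. A completer last dosed at Week 142 would have 1009 − 995 = 14 days covered by the Week 144 visit and excluded by SAP 8.5.

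**Weight of one subject.** With about 20 subjects, one subject missing from a drug's row changes its overall percentage by 1/20 = 5 points, and by more in the separate naïve, IST and rollover summaries that SAP 8.1 requires.

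**The case against.** The case for leaving the text alone is substantial. Counting concomitant medication from first to last dose is a common convention, and the protocol sets no analysis window for medications, so SAP 8.5 contradicts no protocol rule. Protocol 7.6.6.1 describes treatment-emergent events as those with onset during treatment; read strictly, that closes the adverse event window too, and the missing element would be a TEAE end date. The 14 days in SAP 5.8 belong to a duration formula and set no period for medications. Nothing is lost from the record: SAP 8.1 puts all CRF data in listings, and with about 20 subjects these can be read one by one.

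Most of this limits the point without removing it. The SAP definition that governs the TEAE tables has no end, so the two sets of tables do differ as written, and the protocol's narrower wording is a further reason to state the date.

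Several stronger readings are tempting and are not supported:

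- That treatment for the reactions that end therapy disappears. The last-dose day is inside the window, so same-day treatment is tabulated. Protocol 7.4.2.1 calls for an antihistamine before every infusion and allows antipyretics, H2 blockers or steroids; any of these already used on treatment is counted.
- That the missing drugs are concentrated in subjects who stop because of an adverse event. The documents give neither a discontinuation rate nor a rate of medication after the last dose, and protocol 7.4.3 reports no drug-related infusion reactions in the Phase 1/2 study to that date.
- That 67% or 97% of medications are lost. These are shares of calendar days, large because the denominator is short, and the one- and two-infusion cases are illustrations.
- That a full 30 days of medication data already exists for everyone. The Termination Visit may come earlier than Day 30, and completers do not have one.

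**Conclusion.** The point holds as a minor one. As written, SAP 8.5 leaves a drug that is new to the subject and first taken after the last-infusion day out of every summary table, while SAP 8.8.1 can count the event it was given for. The gap is at most 30 days per subject, and it matters mainly for subjects with a Termination Visit. For completers dosed at Week 144 it is small or nil. The percentages assume that TEAEs are counted up to the protocol's 30-day collection limit, and they bound time only; how many subjects or drugs are affected cannot be derived from the documents. No test or efficacy estimate depends on this table, and the records remain in the listings. It still merits correction because it drops recorded data from a named safety measure by an explicit rule and is easy to put right.

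**What to change.** In SAP 8.5, define concomitant medication as any medication taken from the first CL202 dose through the end of recorded follow-up, up to 30 days after the last CL202 dose. Flag drugs first taken after the last dose, or tabulate them as a separate post-treatment category if the on-treatment table is to stay as it is. In SAP 8.8.1, state the same end date for TEAEs and reconcile it with protocol 7.6.6.1.

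The nominal medication window would then match the TEAE window: 45 days instead of 15 for a last infusion at Week 2, and 1039 instead of 1009 for Week 144. The cost is a sentence in each of the two SAP sections and one programming flag, with no added visit. The drawback is that capture after the last visit may be incomplete, especially for completers; a table footnote should say so.
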